#### 4.2.5 Descriptive Analysis

Descriptive statistics for DRSS including change from baseline will be provided. Graphs displaying DRSS versus time will be generated. In addition, individual plots by stratum (DRSS at baseline) and treatment group will be presented. Furthermore, graphs for changes of DRSS at 12, 24, 48 weeks of treatment versus baseline will be provided.

• Descriptive statistics of DRSS including change to baseline will also be broken down by the subgroups defined above and by country (US vs. Non-US).

#### 4.3 Secondary Endpoint Analysis

#### 4.3.1 Secondary Endpoints

#### **4.3.1.1 Definition of Endpoints**

#### '≥/< x steps improvement/deterioration in DRSS (for persons)' at 48 (resp. 12, 24) Weeks of treatment (in the study eye)

These endpoints will be assessed using the same methodology described for the primary efficacy endpoint (see Section 4.2.2).

- $\geq 2$  steps improvement in DRSS' at 12, 24 Weeks of treatment in the study eye
- '< 2 steps deterioration in DRSS' at 12, 24, 48 Weeks of treatment in the study eye
- $\geq 1$  step improvement in DRSS' at 12, 24, 48 Weeks of treatment in the study eye
- $\geq 3$  step improvement in DRSS' at 12, 24, 48 Weeks of treatment in the study eye
- $\geq 3$  step improvement in DRSS for persons' at 12, 24, 48 Weeks of treatment
- '< 3 step deterioration in DRSS' at 12, 24, 48 Weeks of treatment in the study eye
- '< 3 step deterioration in DRSS for persons' at 12, 24, 48 Weeks of treatment

DRSS for persons will be derived according to Table 6-2.

Responder and non-responder definition for the endpoints above:

- For  $\geq x$  steps improvement in DRSS' endpoints
  - Participants with '≥ x steps improvement in DRSS' will be counted as *responder*
  - Participants with '< x steps improvement in DRSS' will be counted as *non-responder*
- For '< x steps deterioration in DRSS' endpoints
  - Participants with '< x steps deterioration in DRSS' will be counted as *responder*
  - Participants with '\ge x steps deterioration in DRSS' will be counted as *non-responder*

#### Vision-threatening complications at 12, 24, 48 Weeks of treatment in the study eye

Assessment of VTC as secondary endpoint is planned in addition, to correlate the DRSSchange with a clinical outcome parameter in support of the efficacy assessment in this study. VTC are defined as occurrence of any of the following AEs:

- PDR (DRSS  $\geq 61$ )
- Any ocular neo-vascularization (retinal or anterior-segment neovascularization)
- Center-involved (central ETDRS subfield) DME
- Drop of BCVA of 10 letters or more from baseline

Study investigations may be continued after treatment discontinuation, after investigator assessment. Treatment of the VTC should follow local standards and guidelines, at the discretion of the investigator.

#### Number of participants with TEAEs

For the definition of TEAEs refer to section 4.1.5.

## 4.3.1.2 Main Analytical Approach

## $\geq x$ steps improvement/deterioration in DRSS (for persons)' at 48 (resp. 12, 24) Weeks of treatment (in the study eye)

This endpoint will be assessed using the same methodology described for the primary efficacy endpoint (see Section 4.2.2) on the PPS and in addition, as a sensitivity analyses on the FAS.

95% credible intervals and point estimates for the difference between the active and placebo response rates will be provided.

#### Vision-threatening complications at 12, 24, 48 Weeks of treatment in the study eye

VTC will be recorded continuously during the study. Predefined timepoints for assessment are 12, 24, and 48 weeks of treatment. VTC are recorded separately for the study eye and the fellow eye. Separate assessments will be done for the study eye and across both eyes (timepoint when a VTC appears in any eye). These endpoints will be analyzed by the Kaplan-Meier-method on the PPS and in addition, as a sensitivity analyses on the FAS. Confidence intervals will be provided for probability of having a vision threatening event up to these time points. Participants dropping out from the study without a VTC will be censored at the last visit. Furthermore, if deemed necessary, the endpoint VTC in any eye (yes/no) will be analyzed using the same Bayesian analysis described for the primary efficacy endpoint (see Section 4.2.2) on the PPS.

#### Number of participants with TEAEs

For analysis of AEs refer to Section 4.5.2.

## 4.3.2 Subgroup Analyses

The secondary analysis of DRSS for persons will be repeated for the following subgroup:

DRSS for persons at baseline

•  $\leq 53 / 53$  (scale step  $\leq 11$ )

## 4.3.3 Supportive Secondary Endpoints

Supportive secondary endpoints will be analyzed descriptively for the PPS and the FAS and will include the following:

- Changes in DRSS from baseline in the study and fellow eye
- Changes in DRSS for persons from baseline

DRSS for persons will be derived according to Table 6-2.

### Changes in DRSS from baseline in the study and fellow eye

Frequencies for changes of DRSS versus baseline in the study and fellow eye will be provided. Furthermore, frequencies for changes of DRSS for persons versus baseline will be provided. In addition, graphs for changes of DRSS for persons at 12, 24, 48 weeks of treatment versus baseline will be provided.

## 4.4 Other Endpoint Analysis

If not mentioned otherwise, these endpoints will be analyzed by descriptive statistics for continuous variables and frequency tables for categorical variables. Furthermore, these endpoints will be analyzed separately for study eye and fellow eye, if not mentioned otherwise.

## 4.4.1 Best corrected visual acuity

Change in BCVA from baseline: BCVA will be assessed using a modified ETDRS protocol starting 4 meters (AREDS, 1999). Descriptive statistics for visual acuity including change from baseline will be provided using geometric and arithmetic means as defined in Section 4.1.

## 4.4.2 Fluorescein angiography

Change in leakage area on FA: The anatomical state of the retinal vasculature of the study eye (transit eye) and the fellow eye (non-transit eye) will be evaluated by FA. The angiographic images will be evaluated by a study ophthalmologist for individual safety decisions. Fluorescein leakage area will be evaluated using FA. Descriptive statistics including box plots will be provided for the change in quantitative FA assessments from baseline to Week 24 and 48 by treatment group using geometric and arithmetic means as defined in Section 4.1.

## 4.4.3 Optical coherence tomography and OCT-angiography

The following parameters will be assessed, as applicable:

- CRT
- OCT-A perfusion density, vessel density
- OCT-A size of foveal avascular zone in study eyes and across both eyes
- OCT-A-DART scans: assessment of vessel thickness

These will be analyzed separately by study part. Furthermore, only relative changes will be provided for the above-mentioned endpoints.

#### Change in central retinal thickness

CRT will be evaluated using OCT and will be collected at each visit. Data will be provided by the central reading center for central subfield thickness, center point thickness, and total macular volume. The absolute values and relative changes from baseline with 95% CI in these parameters at each visit will be summarized descriptively by treatment group.

#### Change in vessel density, perfusion density, size of foveal avascular zone

Vessel density (skeleton), perfusion density, size of foveal avascular zone will be measured by the central reading center for study eye and the fellow eye. Vessel density and perfusion density are evaluated for the different retinal layers assessed: Superficial Retinal Layer, Intermediate Retinal Layer and Deep Retinal Layer and Retina (cumulative, all layers combined).

Relative changes from baseline will be assessed for study eyes and across both eyes. Furthermore, sub-analyses of relative changes will be done for all (individual) eyes by DRSS at baseline. Parameters will be summarized using number of eyes/participants, arithmetic mean, arithmetic SD, arithmetic CV, minimum, median, maximum. In addition, relative change from baseline with 95% CI will be provided.

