#### 1. Introduction

Runcaciguat (BAY 1101042) is a sGC activator that improved function and retinal structure in pre-clinical DR models.

This PoC study includes a subpart with PK/PD assessments (Part 1). Part 1 enrolls a subset of patients at a more intense investigation in specific study sites. Part 2 is the main PoC part, to be conducted in ophthalmology sites, that enrolls the majority of participants. PoC will be based on the evaluation of outcomes in participants from both parts, which will be running in parallel.

The present study is to be conducted to obtain information on sGC activators by investigating

1. whether runcaciguat improves the diabetic retinopathy score in patients with moderately severe to severe NPDR

and to

2. explore the PK/PD relationship of runcaciguat on retinal perfusion

This SAP describes the final analysis of the study. No statistical interim analysis will be performed. TLF specifications are contained in a separate document. The analysis of Pop-PK data will not be described here but will be done in a separate analysis plan.

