#### **Inferential Statistics**

Biomarkers will be assumed log-normally distributed. Therefore, biomarker values will be log-transformed for inferential analyses (unless specified otherwise). The change to baseline of log-transformed measurements is equivalent to the log-transformed ratio-to-baseline:

$$log(BM) - log(BM_{bl}) = log\left(\frac{BM}{BM_{bl}}\right)$$

In order to analyze the impact of treatment on the log-transformed biomarker ratio-to-baseline levels over time ( $\Delta BM._{time}$ ), a linear mixed model will be utilized with  $\Delta BM._{time}$  levels post-dose as the dependent variable and corresponding (log-transformed) biomarker baseline level,

intervention group, visit and the interaction of intervention group and visit as the independent variables:

 $\Delta BM_{.time} \sim BM_{.BL}$  + intervention group + visit + intervention group \* visit + error(within subject) + error(residual)

A similar linear mixed model will be applied as sensitivity analysis for the absolute difference to baselines of biomarkers without log-transformation.

The subject information will enter the model as a random effect, which will be modelled as an individual random intercept, to account for repeated measures per patient. Time related dependencies per participant will be modelled using an autoregressive correlation structure of order one [AR(1)]. The structure of the covariance matrix might be adapted, e.g., in case of convergence problems.

In addition, least-square means will be calculated and back-transformed (only if biomarkers are log-transformed) per intervention group as well as for treatment effect (difference between intervention group and placebo) and reported with 95% CI and p-value for each time points and across all time points.

Plots of least-square means (back-transformed, if required) for ratios and changes to baseline per intervention group, as well as the treatment effect, at each time point and 95% CI will be provided.

Further analyses may include a separate analysis for each runcaciguat maintenance dose level that was reached during titration.

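### SAP 4.4.3 plans no baseline-adjusted drug-placebo estimate for retinal thickness or OCT-A, although SAP 4.6.3 fits that model to the blood biomarkers

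*SAP*

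**What the plan says.** SAP 4.4 sets the default for this group of endpoints: unless stated otherwise, "these endpoints will be analyzed by descriptive statistics for continuous variables and frequency tables for categorical variables". Within it, SAP 4.4.3 covers CRT and OCT-A and adds: "These will be analyzed separately by study part. Furthermore, only relative changes will be provided for the above-mentioned endpoints".

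- **CRT:** "The absolute values and relative changes from baseline with 95% CI in these parameters at each visit will be summarized descriptively by treatment group".
- **Vessel density, perfusion density, foveal avascular zone:** "Parameters will be summarized using number of eyes/participants, arithmetic mean, arithmetic SD, arithmetic CV, minimum, median, maximum". Then: "In addition, relative change from baseline with 95% CI will be provided". Retinal vessel flow is handled the same way.

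SAP 4.1.9 defines relative change as the post-dose value over the baseline value and ties it to variables taken as log-normal. SAP 4.1.1 adds geometric means where log-normality is assumed. SAP 4.4.3 does not state that assumption. By contrast, SAP 4.4.1 and 4.4.2 name both geometric and arithmetic means for visual acuity and leakage area.

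SAP 4.6.3 has a stronger analysis for HbA1c, cGMP, kynurenine, cystatin C and, optionally, norepinephrine. It uses a linear mixed model "In order to analyze the impact of treatment on the log-transformed biomarker ratio-to-baseline levels over time", with log baseline, arm, visit and arm-by-visit. It reports the drug-placebo effect with a 95% CI and p-value.

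**The concern.** One of the two aims in SAP section 1 is to "explore the PK/PD relationship of runcaciguat on retinal perfusion". Part 1 exists for PK/PD work and to explore OCT-A as a pharmacodynamic marker. The results are meant to inform dose and duration for later compounds of the class.

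For these retinal measures the reader will get two columns of summaries, each with its own interval. Two within-arm intervals are not an interval for the difference between arms. A within-arm change also mixes drug effect with time trends and any bias of the summary statistic. The SAP already has a suitable model and applies it to HbA1c but not to CRT, its neighbour under the same objective in Table 1-1, without giving a reason.

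**Working it through.** **1. The plan's own figure.** No precision or power figure is given for CRT or OCT-A. The only design figure is at least 90% probability of proof of concept on the primary endpoint (35% v 10% response, 40 evaluable per arm, Beta(0.5, 0.5) prior). Exact enumeration of both binomial arms gives 0.903, so it reproduces. Nothing below depends on it.

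**2. Two endpoints under one objective.**

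| | HbA1c (SAP 4.6.3) | CRT (SAP 4.4.3) |
|---|---|---|
| Scale for inference | log ratio to baseline | none; relative change summarised |
| Baseline as covariate | yes | no |
| Repeated-visit model | yes | no |
| Drug-placebo effect with CI | yes | no |

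Three other passages might fill the gap:
- SAP 4.1.1 says that data are generally compared between arms, but it names no estimator, covariate or interval.
- SAP 4.6.2 plots CRT and perfusion against trough concentration by maintained dose. That dose depends on tolerability and blood pressure (protocol 6.5.1), so the plot is not a randomised comparison.
- Protocol 8.4 allows, but does not require, PK/PD models under a separate plan.

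**3. Mean ratio when nothing changes.** Assume independent log-normal errors at the two visits with log-variance s². Then E(post/baseline) = exp(s²) = 1 + CV².
- CV 10%: 1 + 0.01 = 1.01.
- CV 20%: 1 + 0.04 = 1.04.

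Equivalently, with total log-SD S and baseline to follow-up correlation rho, it is exp(S²(1 − rho)). At rho 0.5 this is 1.005 for S = 0.1 and 1.020 for S = 0.2. Under no effect the expectation is the same in both arms, so the drug/placebo comparison is not biased by it. The documents give no CV, SD or rho for these measures; all are assumptions.

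**4. Gain from baseline adjustment.** A change-score contrast has variance proportional to 2(1 − rho), an adjusted one to 1 − rho². The ratio is (1 + rho)/2.

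| rho (assumed) | (1 + rho)/2 | variance saved |
|---|---|---|
| 0.3 | 0.65 | 35% |
| 0.5 | 0.75 | 25% |
| 0.7 | 0.85 | 15% |
| 0.9 | 0.95 | 5% |

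This is before the small cost of estimating the slope.

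**5. Half-widths of the 95% interval for the log drug/placebo ratio.** Half-width = t × S × √v × √(1/n₁ + 1/n₂), where v is 2(1 − rho) unadjusted or 1 − rho² adjusted. The degrees of freedom are N − 2 and N − 3. S = 0.20 is assumed.

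| | rho | unadjusted | adjusted |
|---|---|---|---|
| Part 1, 12 v 6 | 0.5 | 0.212 | 0.185 |
| Part 1, 12 v 6 | 0.7 | 0.164 | 0.152 |
| Both parts, 52 v 46 | 0.5 | 0.080 | 0.070 |
| Both parts, 52 v 46 | 0.7 | 0.062 | 0.057 |

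For OCT-A the pooled rows are a best case, because OCT-A is optional in Part 2 (protocol 8.1.1.5). Structural OCT is scheduled in both parts. Splitting by part costs more precision than omitting the covariate.

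In Part 1 the SE of the baseline difference is √(1/12 + 1/6) = 0.50 SD. A chance imbalance above 0.5 SD therefore has probability 0.32.

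**6. What an unrestricted model would produce.** Two densities × four vascular regions + foveal avascular zone + flow = 10 OCT-A parameters. Part 1 schedules OCT-A at Visits 3 to 16, which is 14 post-baseline visits. 10 × 14 = 140 contrasts, of which 0.05 × 140 = 7 would be expected to exclude no effect by chance.

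**The case against.** The best defence is that description suits this tier. CRT is an "other" endpoint, and the OCT-A measures are not named in the objectives table. Protocol 9.4.6 plans only summary statistics for pharmacodynamics, so the SAP does not conflict with the protocol. That stands, and it limits the weight of the point.

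Four stronger readings are tempting, and the documents do not support them:
- **That the study's second aim is the drug effect on perfusion.** The stated aim is to explore a PK/PD relationship. A drug-placebo contrast supports it but is not the same thing.
- **That placebo and baseline go unused.** Baseline is the denominator of every relative change. CRT is summarised by arm, and SAP 4.1.1 says that arms are generally compared. Only the adjusted contrast is missing.
- **That ratio bias undermines the comparison of arms.** Under no effect it is equal in expectation in both arms, so it matters only for a within-arm interval read against 1.
- **That the SAP expressly averages OCT-A ratios arithmetically.** It lists arithmetic statistics for the parameters and then adds the relative change with a CI, without naming the mean behind it. Arithmetic averaging is the natural reading, but it is inferred.

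It is also fair to object that a full arm-by-visit model for every parameter would yield many chance findings against six planned placebo participants in Part 1. That stands, and the fix must limit the set.

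**Conclusion.** The point holds as a gap in the analysis, and it is a minor one. For CRT and OCT-A the SAP commits to no baseline-adjusted randomised estimate, while it does so for blood biomarkers under the same objective. Adjustment is worth 25% of the contrast variance at rho 0.5 and 15% at rho 0.7. An arithmetic within-arm ratio would sit about 1% to 4% above 1 under no change at a test-retest CV of 10% to 20%. The textual gap needs no assumptions. These sizes rest on assumed rho and CV, and the half-widths on an assumed log-SD of 0.20. The proof-of-concept decision is not touched.

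**What to change.** In SAP 4.4.3, for CRT and a short pre-named set of study-eye OCT-A parameters and visits:

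1. Apply the 4.6.3 model: log ratio to baseline on log baseline, arm, visit and arm-by-visit.
2. Report the geometric mean ratio per arm and the drug/placebo ratio with 95% CI, labelled exploratory and without multiplicity adjustment.
3. Wherever Part 2 data exist, also give an estimate pooled over Parts 1 and 2 with part as a factor, since allocation is 2:1 in Part 1 and 1:1 in Part 2. SAP section 3 already plans pooling in general.
4. Use geometric summaries for relative change. The remaining parameters and the both-eye summaries can stay descriptive.

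The cost is SAP wording and reuse of a model program that 4.6.3 already needs; no new data or visits are required. The downside is additional exploratory contrasts, some of which will exclude no effect by chance. The short pre-named list keeps their number small.

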#### Change in retinal vessel flow

Retinal vessel flow will be measured by the central reading center from OCT-A DART scans for study eye and the fellow eye.

Relative changes from baseline will be assessed for study eyes and across both eyes. Furthermore, sub-analyses of relative changes will be done for all (individual) eyes by DRSS at baseline. Parameters will be summarized using number of eyes/participants, arithmetic mean, arithmetic SD, arithmetic CV, minimum, median, maximum. In addition, relative change from baseline with 95% CI will be provided.

### 4.4.4 Slit lamp biomicroscopy (anterior and posterior segment)

Abnormal findings will be recorded in the eCRF as either MH or AE, as applicable, and will be analyzed analogously.

#### 4.4.5 **Tonometry (intraocular pressure measurement)**

Descriptive statistics for intraocular pressure including change from baseline will be provided using arithmetic means. The used methods will be listed only.

#### 4.5 Other Safety Analyses

The secondary objective of the study is to investigate the safety and tolerability of runcaciguat in patients with NPDR. All safety analyses will be performed on the SAF, if not stated otherwise. Participants will be analyzed according to the treatment they actually received.

#### 4.5.1 Treatment Compliance, Duration and Exposure

Tables will be presented for the FAS and PPS.

Frequency tables and summary statistics will be presented for total dose, treatment dose per week, and treatment duration (absolute duration and frequencies with weekly intervals). In addition, treatment compliance will be summarized presenting the percent of tablets that were actually taken out of the planned number of tablets. Frequencies of participants showing compliance <80%, 80-120%, and >120% of the planned tablets will be presented.

The frequencies of dose modifications will be presented by treatment group and visit, especially to assess the escalation, maintenance, reduction, and withdrawal of doses, including the reasons for maintenance, reduction, or withdrawal. Furthermore, the frequency of participants being treated on a certain dose level will be presented by treatment group, visit and dose level to assess the titration level being reached during up-titration and in the maintenance phase.

A listing with the actual dose levels or sham-titration levels for each visit will be presented to get an overview of the individual titration schemes.

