9.4.5 Other safety analysis

All safety analyses will be made on the Safety Population. A detailed description will be given in the statistical analysis plan.

For the secondary objective (safety) of the study, the following additional endpoints will be considered and analyzed:

- Laboratory parameters
- Vital signs
- Electrocardiography

Quantitative data will be described by the following summary statistics: arithmetic mean, standard deviation, median, minimum and maximum. These summary statistics will be presented by treatment for the original data as well as for the difference to baseline. Frequency tables will be provided for qualitative data. Laboratory data outside the reference

09 FEB 2023 Page: 64 of 95

range will be listed and flagged with 'L' for low and 'H' for high. Additional tables with all abnormal values will be presented.

Graphical displays of individual data as well as mean values with standard deviation will be included.

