#### Intercurrent events:

- Dropout due to a VTC in the study eye: *composite variable strategy* (analyze study participant as non-responder)
- Dropout ...

... before Visit 9 (week 12) composite variable strategy (analyze study participant as non-responder)

... after Visit 9 (week 12) with EoT DRSS assessment performed within 4 weeks of treatment discontinuation

while on treatment strategy (use the last available DRSS assessment (LOCF)

... after Visit 9 (week 12) with EoT DRSS assessment performed more than 4 weeks after treatment discontinuation

*while on treatment strategy* (use the last available DRSS assessment prior to treatment discontinuation (LOCF))

• Non-compliance with study intervention, defined as actual drug intake lower than 80% or higher than 120% of the planned drug intake per protocol: *principal stratum strategy* (exclusion from analysis, as an adequate imputation of response information is considered not possible)

The secondary estimand (analysis on FAS) is identical to the primary estimand (analysis on PPS) with the exception that the condition relating to compliance is not included.

Version 3.0

The other estimand (analysis on PPS) is defined below:

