### 3. Analysis Sets

Final decisions regarding the assignment of participants to analysis sets will be made during the review of study data and documented in the final list of important deviations, validity findings and assignment to analysis sets.

For the purposes of analysis, the following analysis sets are defined in Table 3-1. The same definitions apply for Part 1 and Part 2.

Participant analysis set	Assignment rule	
Full analysis set (FAS)	All participants of the respective study part randomized to treatment who fulfilled in/exclusion criteria.	
Per protocol set (PPS)	All FAS participants of the respective study part without validity findings.	
Pharmacokinetic analysis set (PKS)	All participants of the respective study part with PK information not affected by relevant validity findings and with at least one valid post-dose plasma concentration.	
Safety analysis set (SAF)	All participants of the respective study part who took at least one dose of study intervention.	

It is planned to pool the data of participants from Part 1 and Part 2 for analysis, without further stratification by analysis parts, considering that selection criteria and recruitment time periods were identical and all study procedures in Part 2 were performed also in participants enrolled in Part 1. Participants will be analyzed by their actual treatment to which they were treated for most of the time (i.e., placebo or runcaciguat, irrespective of the planned dose they were planned to be titrated to).

The detailed definitions of validity findings and the assignment of participants to the analysis sets will be based on the ACIR document.

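### SAP 4.5.1 omits the safety set from its exposure, dose-level and dose-modification tables, so a treated but ineligible participant is in the adverse-event tables and in none of these summaries

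*SAP*

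**What the plan says.** SAP 4.5.1 falls under the heading for other safety analyses. It covers total dose, dose per week, treatment duration, compliance in three bands (below 80%, 80 to 120%, above 120%), dose modifications by visit with reasons, and the dose level reached by visit. On the population it says only: "Tables will be presented for the FAS and PPS".

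The parent section, SAP 4.5, sets the default: "All safety analyses will be performed on the SAF, if not stated otherwise". The adverse-event tables in SAP 4.5.2 name no other set, so they use the SAF. Protocol 9.4.5 has the same general rule: "All safety analyses will be made on the Safety Population".

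SAP Section 3 defines the sets:
- FAS: "All participants of the respective study part randomized to treatment who fulfilled in/exclusion criteria".
- PPS: "All FAS participants of the respective study part without validity findings".
- SAF: "All participants of the respective study part who took at least one dose of study intervention".

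It adds: "The detailed definitions of validity findings and the assignment of participants to the analysis sets will be based on the ACIR document". The ACIR is a separate document and is not part of the protocol or SAP.

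Under the primary estimand in SAP 1.1, which is analysed on the PPS, non-compliant participants are excluded. Non-compliance is "defined as actual drug intake lower than 80% or higher than 120% of the planned drug intake per protocol". The secondary estimand, on the FAS, differs only in leaving out that condition.

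**The concern.** Tolerability of a titrated vasodilator is judged from two kinds of table read together: how many participants had adverse events that changed their dosing, and how many reached, held, reduced or stopped each dose, and why. Here the first kind is on the SAF and the second on the FAS and PPS. Neither of the latter sets contains all treated participants.

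Those left out are dosed participants who turn out not to meet the selection criteria. Several exclusion criteria concern blood pressure, renal function and prohibited medication, so such a participant could matter for safety. Their event would be tabulated while their dose, duration and dose changes would not. A reader comparing, say, adverse events leading to dose reduction with the dose-reduction table would find different denominators and possibly different counts, with no explanation in the SAP.

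The choice also differs from the SAP's other descriptive tables. Baseline characteristics (6.2) are planned for the FAS, PPS, SAF and PKS. Medical history (6.4) and medication (6.5) are on the SAF. The SAP gives no reason for omitting the SAF from exposure.

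**Working it through.** The plan gives no figure on this point. The check is set logic on the SAP Section 3 definitions, followed by a simple statement of size.

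**Step 1. Where each type of participant appears.**

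| Participant | SAF (4.5.2 tables) | FAS | PPS | 4.5.1 summary tables |
|---|---|---|---|---|
| Dosed, eligible, no validity finding | yes | yes | yes | both versions |
| Dosed, eligible, validity finding | yes | yes | no | FAS version |
| Dosed, ineligible | yes | no | no | none |
| Randomised, eligible, never dosed | no | yes | depends on ACIR | at least the FAS version |

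The third row is the gap. Because the PPS is a subset of the FAS, running both versions does not close it. The fourth row is the reverse mismatch, but it should be rare: randomisation and first dose are both scheduled at Visit 2 (Protocol 1.3).

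**Step 2. Size.** The documents do not give the number in SAF minus FAS; call it m for the runcaciguat arm. The planned arm is 12 (Part 1) + 40 (Part 2) = 52 (SAP Table 5-1). Assume all 52 are dosed. The share of the arm's adverse-event denominator that is missing from the 4.5.1 tables is m/52. The range for m is an assumption:

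| m | FAS (52 − m) | Share missing, m/52 |
|---|---|---|
| 0 | 52 | 0% |
| 1 | 51 | 1.9% |
| 2 | 50 | 3.8% |
| 3 | 49 | 5.8% |
| 5 | 47 | 9.6% |

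**Step 3. Where these participants still appear.** SAP 4.5.2 divides the number with events at a dose level by the exposure time of everyone on that level, on the SAF by default, so their exposure time is in those rates. SAP 4.5.1 also plans a listing of dose levels by visit with no set named. SAP 6.3 reports permanent treatment discontinuations with reasons and does not limit them to the FAS. What is missing is the summary of dose, duration, level reached and dose changes.

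**Step 4. The PPS compliance table.** If the 80 to 120% rule is how compliance enters the PPS, the two outer compliance rows are empty by construction. SAP 1.1 points that way, since compliance is the only stated difference between the PPS and FAS estimands. SAP Section 3, however, leaves validity findings to the ACIR. SAP 4.2.2 can also be read as a compliance filter applied on top of the PPS, in which case the PPS table could still show non-compliant participants. Empty rows are therefore likely but not certain.

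**The case against.** The strongest reply is that this is a permitted, descriptive choice with little consequence. The SAF default in SAP 4.5 allows exceptions, and 4.5.1 states one. Protocol 5 bars eligibility waivers and eligibility is checked at Visits 1 and 2, so few dosed participants should prove ineligible. No efficacy result, adverse-event rate or proof-of-concept decision draws on the 4.5.1 tables. Showing compliance on the FAS and PPS also has a purpose, because compliance separates the two estimands. All of this stands, and it limits the weight of the point. It does not remove the mismatch in Step 1.

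Two stronger readings do not stand.

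A reader might infer that the PPS restriction hides intolerance, so that participants who stopped or interrupted drug vanish from the dose-modification tables. The same tables are also run on the FAS, which has no compliance condition, so eligible participants with poor intake, reductions or withdrawals all appear there. Nor is it clear that early stopping counts as intake below 80%. The primary estimand keeps dropouts, as non-responders or by carrying the last value forward, and the SAP does not say whether planned intake runs to Week 48 or to discontinuation. Interruption is also capped at 21 days overall (Protocol 7.1.1). Over 48 × 7 = 336 days that is 21/336 = 6.25%, too little on its own to take a 48-week completer below 80%.

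A reader might also infer an undeclared departure from the protocol, since SAP 4.8 does not mention it. Protocol 9.4.5 follows its general rule with laboratory parameters, vital signs and ECG as the endpoints to be analysed; exposure and compliance are not named. The documents do not clearly support a departure.

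**Conclusion.** The point holds in a narrow form. By the SAP's own definitions, a treated but ineligible participant is counted in the adverse-event tables and in none of the 4.5.1 summary tables, so exposure, titration and dose-modification summaries need not reconcile with the adverse-event tables they help to interpret.

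The size is unknown and probably small. Each such participant is 1.9% of the planned runcaciguat arm; the 0 to 9.6% range in the working rests on an assumed 0 to 5 participants and on all 52 being dosed. If nobody dosed is found ineligible, this gap is empty. The PPS compliance question depends on the ACIR and does not affect the conclusion. This is a low-cost improvement to the presentation of safety data. It does not correct any planned estimate.

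**What to change.** In SAP 4.5.1, replace the sentence on populations with: *Tables on exposure, treatment duration, dose level and dose modifications will be presented for the SAF by treatment received; compliance will be presented for the SAF and FAS.* If a PPS version is wanted, keep it and label it as a description of that set only.

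The cost is one SAP sentence, the matching entries in the table specifications, and a rerun of the same programs on another set. No new data are needed and no efficacy analysis changes.
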